6.2.20 Patient Global Impression of Change

Patient Global Impression of Change (PGI-C) is a 7-point scale (1 to 7; where 1 corresponds to ‘very much improved’, 4 is ‘no change’, and 7 is ‘very much worse’) that captures the subjects’ impression of their overall change since the beginning of the study to specific time points during the study.

For the analysis, subjects will be classified as either responders, that is, a PGI-C response of 1 (‘very much improved’) or 2 (‘much improved’), or non-responders, that is, all other PGI-C responses (recorded as 3, 4, 5, 6 and 7) at Week 12. Subjects will be classified as non-responders if their PGIC assessments at Week 12 are missing.

6.2.21 Fibromyalgia Impact Questionnaire – Revised

Fibromyalgia Impact Questionnaire – Revised (FIQR) is questionnaire consisting of 21 individual questions in an 11-point numeric rating scale from 0 to 10 (where 10 correspond to ‘worst’). The FIQR is divided into three domains: ‘function’ (containing 9 questions), ‘overall impact’ (containing 2 questions), ‘symptoms’ (containing 10 questions). The total FIQR score is calculated as the sum of three modified domain scores: the summed score for function divided by 3, the

summed score for overall impact, the summed score for symptoms divided by 2. Higher FIQR scores indicate greater disease severity and impaired physical function.

6.2.22 Patient Reported Outcomes Measurement Information System

6.2.22.1 Patients Reported Outcome Measurement Information Systems – Fibromyalgia (PROMIS_{FM}) Fatigue Profile

The PROMIS_{FM} fatigue profile is a 16-question instrument in a 5-point numeric rating scale (1 to 5; where 1 corresponds to ‘Not at all’, 2 corresponds to ‘A little bit’, 3 corresponds to ‘Somewhat’, 4 corresponds to ‘Quite a bit’, 5 correspond to ‘Very much’) that examines the fatigue experience and intensity of impact of fatigue in social, cognitive, and motivation subdomains. Scoring is done by calculating raw scores for each subdomain by summing subject’s answers. Missing values are not allowed and if any data missing for a domain then total raw score will not be calculated. After raw scores are calculated a scoring table will be used to translate the total raw score into a T-score for each subject.

6.2.22.2 Patients Reported Outcome Measurement Information Systems (PROMIS) Sleep Disturbance

The PROMIS sleep disturbance is an 8-question instrument in a 5-point numeric rating scale (1 to 5; where 1 corresponds to ‘Not at all’, 2 corresponds to ‘A little bit’, 3 corresponds to ‘Somewhat’, 4 corresponds to ‘Quite a bit’, 5 correspond to ‘Very much’) that assesses sleep disturbance in subjects 18 years and older. Scoring is done by calculating total raw scores for each domain by summing subject’s answers. Missing values are not allowed and if any data missing for a domain then total raw score will not be calculated. After raw scores are calculated a scoring table will be used to translate the total raw score into a T-score for each subject.

6.2.22.3 Patients Reported Outcome Measurement Information Systems (PROMIS) Physical Function

The PROMIS sleep disturbance is an 12-question instrument in a 5-point numeric rating scale (1 to 5; where 1 corresponds to ‘Unable to do’, 2 corresponds to ‘With much difficulty’, 3 corresponds to ‘With some difficulty’, 4 corresponds to ‘With a little difficulty’, 5 correspond to ‘Without any difficulty’) that measures the self-reported performance of physical activities among fibromyalgia patients. If subject answered ‘YES’ in the first question ‘Can you walk 25 feet on a level surface

(with or without support)?”, then he/she filled all the following 12 questions. If subject answered ‘NO’ then only 6 further questions were filled. Scoring is done by calculating total raw scores for each domain by summing subject’s answers. Missing values are not allowed and if any data missing for a domain then total raw score will not be calculated. After raw scores are calculated a scoring table will be used to translate the total raw score into a T-score for each subject.

6.2.23 [REDACTED]

6.2.24 Sheehan-Suicidality Tracking Scale

The standard version of the Sheehan-Suicidality Tracking Scale (S-STS) is a 16-item scale that assesses the seriousness of suicidality phenomena on a Likert-type scale (0 to 4; where 0 corresponds to “not at all” and 4 corresponds to “extremely”). It also assesses the frequency of key phenomena and the overall time spent in suicidality. [REDACTED]

[REDACTED]

[REDACTED]

[REDACTED]

[REDACTED]

6.2.25 Liver Function Abnormalities

Any subject meeting the following criteria will be identified and results will be listed separately for these subjects:

- ALT or AST $>3\times$ ULN or Bilirubin $>2\times$ ULN

Where ALT = Alanine Aminotransferase, AST = Aspartate Aminotransferase, and ULN = Upper Limits of Normal.

6.3 Conventions

6.3.1 Medical Coding

Adverse events and medical history will be coded using the Medical Dictionary of Regulated Activities (MedDRA) Version 24.1 (or higher). Conditions will be assigned to a primary system organ class (SOC) and preferred term (PT) based on the Investigator-reported verbatim term.

Any medications taken (other than study drug) will be coded using the World Health Organization Drug Dictionary (WHO Drug) September 2021 Version (or higher). Medications (both prior and concomitant) will be assigned to an Anatomical Therapeutic Chemical (ATC) Level 3 drug classification and Preferred Name based on the medication name reported on the eCRF.

6.3.2 Data Handling

All clinical data programming will be performed using SAS® statistical software package (Statistical Analysis System, Version 9.4 or higher) and based on Clinical Data Interchange Standards Consortium (CDISC) data standards.

Study Data Tabulation Model (SDTM) programming will follow SDTM version 1.7 together with SDTM implementation guide 3.3. Analytical Data Model (ADaM) programming will follow ADaM implementation guide 1.1. Specifications for SDTM and ADaM datasets are described in a separate document.

6.3.3 Validation Methods

All programming of datasets and outputs will be validated by independent programming (IP) of values, programmatic comparison and manual review of format compared to the SAP and agreed shell template. Figures will be validated by manual review of format and visual inspection of graphical display compared to tabulated data. Independent programming by a Statistician (Stat IP) will be performed for all analyses relating to the primary endpoint.

6.3.4 Descriptive Statistics

Continuous variables will be summarized by the number of non-missing observations, mean, median, standard deviation, and minimum and maximum.

Categorical variables will be summarized by presenting the frequency and percent. Percentages will be based on the number of non-missing observations or the subject population unless

otherwise specified. For each variable, all categories will be shown. Zero frequencies (but not the percent) within a category will be presented.

Incidences of adverse events, medical history and concomitant medications will be reported at the subject level. Subjects can only be counted once within each PT and SOC under the highest severity and most related. Percentages will be calculated using the number of subjects in the treatment group for the Safety Population.

6.3.5 Decimal Places

Decimal places for derived data described in Section [6.2](#) will be determined by the scale of measurement unless otherwise stated. No decimal places will be displayed if the smallest calculated value is ≥ 100 ; 1 decimal place will be displayed when the smallest value is within the interval (10, 100), with 10 being inclusive; 2 decimal places will be displayed when the smallest value is within (1, 10), with 1 being inclusive; and so on for even smaller scales of measurement.

Derived data where it is known in advance the result will be an integer for example day, month, year, number of days and total scores (for rating scales) will be presented with zero decimal places.

For descriptive (summary) statistics, n will be reported as a whole number. Means, medians, and percentiles will be displayed to one more decimal place than the data, dispersion statistics (e.g., standard deviation) will have two more decimal places, and the minimum and maximum will be displayed to the same number of decimal places as reported in the raw data. Percentages will be displayed with one decimal place. All data presented in the individual subject listings will be as recorded on the eCRF.

P-values will be quoted to 3 decimal places. P-values < 0.001 will be presented as p<0.001.

6.3.6 Data Displays

All clinical data tabulations, figures and listings will be generated as individual Rich Text Format (.rtf) files using SAS (Version 9.4 or higher)¹. Data summaries, statistical analyses and graphical analyses will be reported within Section 14 of the CSR and individual subject data listings within [Appendix 16.2](#) of the CSR. Specifications (shells) for Tables, Figures and Listings will be provided as a separate document.

Subject disposition, baseline characteristics, demographic data, treatment exposure, compliance, medical history, concomitant medication, and adverse event data will be presented by treatment group and overall.

Other safety and efficacy data will be presented by treatment group only.

Treatment group labels will be displayed as follows:

NYX-2925 50 mg (N=XX)	NYX-2925 100 mg (N=XX)	Placebo (N=XX)
--------------------------	---------------------------	-------------------

Listings will be sorted in the following order: treatment group, subject, parameter, and visit unless otherwise stated. All data will be listed. For some listings, subjects who were not randomized will be presented but will be displayed after the randomized treatment groups

6.4 Subject Disposition

Subject disposition will be summarized as follows:

- The number of subjects, who entered the study, were randomized and who are in each analysis population will be summarized by treatment group and overall, for all subjects
- The number of subjects who were randomized in error and received no IMP will be summarized overall
- The number of subjects who failed screening and the reasons for failure will be tabulated for all subjects
- The number of early withdrawals and the reasons for withdrawal will be tabulated by treatment group and overall, for the Screened Population
- The number of subjects who completed the study will also be tabulated by treatment group and overall

For participants who were re-screened, reason for screen failure will be taken from the most recent screening attempt. Data from both attempts will be listed.

6.5 Protocol Deviations

Protocol deviation categories will be tabulated by treatment group and classification (Major, Minor) for the Safety Population. Additionally, COVID-19 related protocol deviations will be identified. A listing of protocol deviations will be provided within Appendix 16.2 of the CSR.

6.6 Baseline Comparability

The comparability of treatment group with respect to subject demographics and baseline characteristics will be assessed in a descriptive manner.

Standard continuous or categorical variable summaries will be presented by randomized treatment group for the following variables based on the Safety Population.

- Age (years)
- Sex (male/female)
- Fertility status (for female subjects only)
- Ethnicity
- Race
- Height (cm), weight (kg), BMI (kg/m²)
- Physical and neurological examination (Normal/Abnormal, Not Clinically Significant [NCS], Abnormal, Clinically Significant [CS]) by body system at screening

6.7 Medical History

Separate tabulations of prior and ongoing conditions at screening will be presented by treatment group and overall for the Safety Population. Conditions will be presented by Medical Dictionary of Regulated Activities (MedDRA) Version 24.1 primary system organ class and preferred term.

6.8 Prior and Concomitant Medications

Separate tabulations will be produced for prior and concomitant medications presented by treatment group and overall, for the Safety Population. For reporting purposes, prior medications are defined as all medications taken within 30 days of the Screening visit but stopping before the date of first dose of study drug. Concomitant medications are defined as medications taken on or after the date of first dose of study drug, including medications initiated prior to the first dose of study drug and continuing after first dose of study drug. Medications for which a stop date is not recorded will be designated ongoing at end of study. Prior and concomitant medications will be summarized using Anatomic Therapeutic Chemical (ATC) Level 3 and Preferred Name.

6.9 Exposure to Study Drug

Extent of exposure (number of days of exposure to study drug) will be presented by randomized treatment group for the Safety Population.

6.10 Treatment Compliance

Treatment compliance, calculated as defined in Section [6.2.8](#), will be presented by treatment group per visit interval (Visit 2 to Visit 4, Visit 4 to Visit 5, and Visit 5 to Visit 6) for the Safety Population

6.11 Efficacy Analyses

All statistical tests will be performed using a one-tailed 5% overall significance level as primary analysis. All comparisons between treatments will be reported with one-sided 95% confidence intervals (CI). All analyses will be performed independently on the treatment groups.

All statistical tests will be repeated using a two-sided 5% overall significance level, unless otherwise stated. All comparisons between treatments will be also reported with two-sided 95% CI.

6.11.1 Primary Endpoint

The primary efficacy endpoint is the change from baseline to Week 12 in the weekly mean of the daily NRS score assessing average pain intensity in the past 24 hours. The hypothesis for one-sided testing between NYX-2925 50mg- and placebo- treated groups is as follows:

$$H_0 = \mu_{NYX,50\ mg} - \mu_{placebo} \geq 0 \quad \text{versus} \quad H_1 = \mu_{NYX,50\ mg} - \mu_{placebo} < 0$$

The hypothesis for testing between NYX-2925 100 mg- and placebo- treated groups is as follows:

$$H_0 = \mu_{NYX,100\ mg} - \mu_{placebo} \geq 0 \quad \text{versus} \quad H_1 = \mu_{NYX,100\ mg} - \mu_{placebo} < 0$$

Where $\mu_{NYX,50\ mg}$ denotes the mean change from baseline to Week 12 in the weekly mean of the NRS score in the NYX-2925 50 mg treatment group, $\mu_{NYX,100\ mg}$ denotes the mean change from baseline to Week 12 in the weekly mean of the NRS score in the NYX-2925 100 mg treatment group and $\mu_{NYX,placebo}$ denotes the mean change from baseline to Week 12 in the weekly mean of the NRS score in the placebo group.

The hypothesis for two-sided testing between NYX-2925 50mg- and placebo- treated groups is as follows:

$$H_0 = \mu_{NYX,50\ mg} - \mu_{placebo} = 0 \quad \text{versus} \quad H_1 = \mu_{NYX,50\ mg} - \mu_{placebo} \neq 0$$

The hypothesis for testing between NYX-2925 100 mg- and placebo- treated groups is as follows:

$$H_0 = \mu_{NYX,100\ mg} - \mu_{placebo} = 0 \quad \text{versus} \quad H_1 = \mu_{NYX,100\ mg} - \mu_{placebo} \neq 0$$

6.11.1.1 Estimand

The primary efficacy analysis will evaluate the treatment-policy estimand to estimate the improvement (reduction) from Baseline in the weekly mean of the daily NRS score in subjects in the modified ITT population not discontinuing treatment early due to an AE or lack of efficacy through Week 12.

The following four attributes describe the estimand that will be used to define the treatment effect of interest for the primary efficacy analysis:

- Population = Subjects meeting the protocol-specified inclusion/exclusion criteria, who received at least one dose of study drug and who have at least one post-baseline assessment of the pain intensity NRS.
- Subject-level outcome = Change from baseline in the weekly mean of the daily NRS score assessing average pain intensity in the past 24 hours
- Intercurrent event handling = An intercurrent event is defined as discontinuation of study drug due to an AE or lack of efficacy prior to Week 12. For the analysis, baseline Observation Carried Forward (BLOCF) imputation will be used to impute data for visits after a patient has discontinued randomized treatment due to either of these reasons (even if data is present).
- Population-level summary measure = Difference in least squares (LS) mean change from baseline in the weekly mean of the daily NRS score at Week 12, comparing each dose of NYX-2925 to placebo.

Any missing data at Week 12 that are not preceded by an intercurrent event (i.e., discontinuation of study drug due to AE or lack of efficacy) will remain as missing.

6.11.2 Primary Efficacy Analysis

A one-tailed restricted maximum likelihood (REML)-based mixed model for repeated measures (MMRM) with one sided 95% CI will be utilized to assess the difference between treatment groups with respect to change from baseline to Week 12 in the weekly mean of the NRS score assessing average pain intensity in the past 24 hours.

The MMRM model will have site, treatment group, week, baseline NRS score, and treatment-by-week interaction as terms in the model. The unstructured covariance (UN) will be utilized as the within-subject covariance structure. In the event that the model fails to converge using the UN, the

Fisher scoring algorithm (via the SCORING option of the PROC MIXED statement) will be used to obtain the initial values of covariance parameters, otherwise, no-diagonal factor analytic structure (via the TYPE = FA0(T) option of the REPEATED statement) will be used as another option. When the above strategy fails, the successive univariate regression method will be applied. The Kenward-Roger degrees of freedom correction will also be used for this analysis.

The estimate of the difference between NYX-2925 50 mg versus placebo and NYX-2925 100 mg versus placebo at Week 12 and standard error (SE) will be derived from this model. Observed NRS scores at baseline and at each week, as well as their change from baseline at each week will be presented by treatment groups. The LS means, corresponding SEs, and 95% CI for each treatment group, the treatment difference of LS means, corresponding SEs, 1-sided 95% CI and 1-sided p-value at each week will be presented. The upper limit of the 95% CI of treatment difference will be extracted using ALPHA=0.10 statement for the bound in the unfavorable direction, and the limit in the favorable direction will be set to negative infinity.

The following is the sample SAS code that will be used for this analysis:

```
PROC MIXED DATA= DATAIN;
  CLASS USUBJID TREATMENT WEEK SITE;
  MODEL CHG = TREATMENT WEEK SITE TREATMENT*WEEK BASELINE / DDFM=KR;
  REPEATED WEEK / SUBJECT=USUBJID TYPE=UN;
  * extract two-sided 95%CI of LS MEANS each treatment groups by week;
  LSMEANS TREATMENT*WEEK / DIFF CL;
  * extract one-sided 95%CI of LS MEANS each treatment groups by week;
  LSMEANS TREATMENT*WEEK / DIFF CL ALPHA=0.10;
  RUN;
```

A line plot showing the LS means and 95% CIs of the weekly mean NRS scores from Week 1 through Week 12 for each treatment group will be presented. The two-sided testing will be also performed for primary efficacy analysis and all following sensitivity analyses. The LS means, corresponding SEs, and 95% CI for each treatment group, the treatment difference of LS means, corresponding SEs, 2-sided 95% CI and 2-sided p-value at each week will be presented.

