treatment group difference using a mixed model for repeated measures (MMRM) with factors for study site, treatment, week, treatment by week interaction, and including the baseline value of the response variable as a covariate. Line plots displaying the mean weekly NRS scores from Weeks 1 through 12 for each treatment group will be generated. In these plots, the horizontal axis will reflect the study week and the vertical axis will reflect the average pain score.

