4 SAMPLE SIZE

The planned sample size is a total of 300 randomized subjects with 100 subjects per treatment group. Efficacy analyses will include all subjects who receive at least one dose of study drug and who have at least one post baseline assessment. It is expected that approximately 15% of subjects will be excluded from the efficacy population. A total of 85 subjects per treatment arm will provide approximately 88% power to detect a difference in means of 0.73 for NYX-2925 50 mg or 100 mg versus Placebo group assuming that the common standard deviation is 1.7 without correcting for multiple testing, using one-sided statistical testing with an overall Type I error rate of 0.05.

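### The primary MMRM uses one baseline slope for all 12 weeks, which can cost some precision at Week 12 if that slope drifts over time

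*SAP*

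**What the plan says.** SAP 6.11.2 lists the model terms: "The MMRM model will have site, treatment group, week, baseline NRS score, and treatment-by-week interaction as terms in the model". The sample code agrees: "MODEL CHG = TREATMENT WEEK SITE TREATMENT*WEEK BASELINE / DDFM=KR". BASELINE is not in the CLASS statement and is not crossed with WEEK, so it is a continuous covariate with a single coefficient. Protocol 12.6.1 specifies the same model, "with factors for study site, treatment, week, treatment by week interaction, and including the baseline value of the response variable as a covariate". The post-lock addendum changes imputation wording but not these terms.

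On covariance, SAP 6.11.2 says: "The unstructured covariance (UN) will be utilized as the within-subject covariance structure". The quantity to be read off the model is "The estimate of the difference between NYX-2925 50 mg versus placebo and NYX-2925 100 mg versus placebo at Week 12".

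Week-specific baseline coefficients appear in two other places:
- **SAP 6.11.3.1.** The control-based imputation regresses each week's score separately with baseline among the predictors. The completed data then go back into the common-slope MMRM.
- **SAP 6.11.3.3.1.** The supportive ANCOVA uses Week 12 data only. The addendum (Change 6) says this analysis has no imputation, whereas the primary analysis uses BLOCF after discontinuation for an AE or lack of efficacy.

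**The concern.** The model frees the treatment effect at every week but ties the baseline effect to one value. With an unstructured covariance, generalised least squares weights that one slope toward the weeks that carry most information about it, which are the less variable ones. If variability rises during the trial, those are the early weeks. If change also depends more strongly on baseline later on, the slope used at Week 12 is too shallow. Variation that baseline could have explained then stays in the Week 12 residual.

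What is at stake is the standard error of the two Week 12 contrasts that decide the trial. No planned analysis isolates the restriction, because the ANCOVA differs from the primary analysis in its imputation rule as well as its slope.

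**Working it through.** **1. Reproduce the plan's power.** SAP 4 states: "A total of 85 subjects per treatment arm will provide approximately 88% power to detect a difference in means of 0.73", "assuming that the common standard deviation is 1.7 without correcting for multiple testing", one-sided at 0.05.

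- SE of the difference = 1.7 × √(2/85) = 1.7 × 0.1534 = 0.2608.
- 0.73 / 0.2608 = 2.799.
- One-sided power = Φ(2.799 − 1.645) = 87.6%. The noncentral t gives 87.4%.
- Two-sided power = Φ(2.799 − 1.960) = 79.9%.

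The stated figure of about 88% reproduces.

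**2. Formula for the loss.** Let b_w be the true slope of change on baseline at week w, s_12 the Week 12 residual SD with its own slope, and SD_B the baseline SD. In large samples the common slope b* is the inverse-covariance-weighted average of the b_w. Then:

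- Week 12 variance ratio (common versus week-specific slope) = 1 + (b_12 − b*)² × SD_B² / s_12².

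If all b_w are equal, b* = b_12 and the ratio is exactly 1.

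**3. Inputs that the documents do not give.** Weekly slopes, baseline SD, weekly SDs and correlations are all assumed: slope drift from Week 1 to Week 12 of 0.15 to 0.30, baseline SD 0.8 to 1.3, Week 1 residual SD 0.8 to 1.0 rising to 1.7, and several correlation patterns.

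**4. Where the common slope lands.** With SDs rising in this way (and over somewhat wider ranges), the first three weeks carry a net 63% to 138% of the weight, median about 100%. Net weights above 100% arise because some later weeks get negative weight. In a simulation with slopes of −0.10 at Week 1 and −0.40 at Week 12, the common slope averaged −0.127. A model with week-specific slopes recovered −0.398 at Week 12.

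**5. Worked example.** Take b_12 = −0.40, b* = −0.127, SD_B = 1.2, and a total (unadjusted) Week 12 SD of 1.7.

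- s_12² = 1.7² − (0.40 × 1.2)² = 2.890 − 0.230 = 2.660.
- Added variance = 0.273² × 1.2² = 0.107.
- Ratio = 1 + 0.107/2.660 = 1.040, so the SE is 2.0% larger.
- Power is 89.9% with week-specific slopes and 88.8% with the common slope.

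Both exceed the 87.6% in step 1, which takes no explicit credit for baseline adjustment.

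**6. Ranges.**

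| Assumption | Effect of the common slope at Week 12 |
|---|---|
| No drift | none (simulated SE ratio 1.000) |
| Drift 0.15–0.30, rising SDs, baseline SD 0.8–1.3 | variance +0.3% to +10%, median about 1–4% depending on the drift |
| Drift 0.15–0.30, Week 1 SD 0.8–1.1, baseline SD 0.8–1.2 | SE +0.2% to +3.8%; 0.1 to 2.0 power points |
| Drift 0.15–0.30, weekly SDs flat | variance about +1% or less |
| Drift 0.45, baseline SD 0.8–1.5 | SE +1.6% to +14.2%; 0.9 to 6.9 power points |

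At the 10% end, if 1.7 is taken as the residual SD after full adjustment, power is Φ(2.799/√1.10 − 1.645) = 84.7%, a loss of 2.9 points. At 4% it is 86.4%, a loss of 1.1 points.

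**7. Bias.** The simulation used 3 × 85 subjects and 25% dropout that was missing at random, without a site term or BLOCF. Treatment estimates from the two models agreed within 0.012. SE ratios were 1.007, 1.019 and 1.071 for drifts of 0.20, 0.30 and 0.45.

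**The case against.** The strongest reply is that nothing in the documents shows any drift. Without it there is no loss, and a grid in which every setting drifts has the loss built in. That stands, and it is why the point is conditional.

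Two design features could shrink the effect:
- **BLOCF** sets change to zero after discontinuation for an AE or lack of efficacy, which pulls later slopes toward zero. As an illustration, if 15% of subjects were set to zero regardless of baseline, a Week 12 slope of −0.40 would become 0.85 × −0.40 = −0.34. That reduces the drift without removing it.
- **Randomization** is gated on the seven-day mean pain score, which may narrow the spread of baseline values. The thresholds are masked, so the baseline SD cannot be checked.

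It can also be said that the ANCOVA already supplies a Week 12 slope. It does, but without BLOCF it is not a like-for-like check.

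Three stronger readings are tempting and are not supported:
- **That power falls below the stated 88%.** SAP 4 does not say whether the SD of 1.7 is before or after baseline adjustment. If it is the unadjusted SD, then at drifts of 0.15 to 0.30 the planned model still has 87.6% to 89.9%, against 87.8% to 91.1% with the extra term.
- **That the handling of missing Week 12 data is harmed.** The simulation showed no material bias, and the imputation in 6.11.3.1 is not tied to one slope.
- **That the same loss applies to FIQR and PROMIS.** These are scheduled after baseline only at Weeks 4, 8 and 12, so the pull from Weeks 1 to 3 does not carry over, and no loss was computed for them.

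**Conclusion.** The restriction is real and appears in both documents, but the loss is conditional. It needs a baseline slope that changes over time, and it becomes appreciable mainly when early weeks are less variable. Neither condition can be checked from the documents. Under moderate drift the price at Week 12 is modest, usually no more than 2 power points. It grows if drift reaches 0.45 and disappears if there is none.

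This is a cheap missed gain in efficiency. It is not an error in the power calculation, a source of demonstrated bias, or a threat to the Type I error rate. It is worth correcting because in large samples the extra term can only match or improve Week 12 precision.

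**What to change.** In a plan of this kind, add BASELINE*WEEK to:
- the MODEL statement in SAP 6.11.2, with matching text in protocol 12.6.1;
- the same MMRM run on each imputed dataset in SAP 6.11.3.1;
- the weekly DSIS MMRM in SAP 6.11.4.2.

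For FIQR and PROMIS the term is optional and would use two parameters. For weekly data it uses 11 (12 slopes instead of one), set against the 12 × 13 / 2 = 78 covariance parameters that the unstructured matrix already needs. No new data are required.

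For this trial the timing limits what can be done. The addendum states that it was written after database lock and unblinding, so the primary model should not be replaced. The term can be fitted as a sensitivity analysis, labelled post hoc, under the same BLOCF rule as the primary analysis. Reporting the estimated baseline slope by week would show whether the drift assumed here occurred.
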